9.9 Discontinuation of Treatment/Study Termination Criteria

If a participant in the trial meets criteria for discontinuation and the Investigator is unable to determine whether the adverse event is related to study treatment, the participant should discontinue treatment and be taken off the treatment phase of the study after discussion with the Medical Monitor. The adverse event should be assessed consistent with the Common Terminology Criteria for Adverse Events (CTCAE) v5.0. Unblinding for individual patients may be warranted after consultation with the Medical Monitor for adverse events of CTCAE grade ≥ 3 .

Study treatment should be permanently discontinued for the following:

- The investigator believes that for safety reasons or tolerability reasons (e.g., AE), it is in the best interest of the participant to discontinue study treatment.
- Any Grade 3 non-skin, drug-related AE lasting > 7 days, or recurs with the following exceptions for hypotension (without associated AEs (e.g., dizziness)), diarrhea, or colitis-related symptoms.

The study must be terminated if any of the following criteria are met:

- Two or more study drug-related ≥ Grade 4 AEs or SAEs (unblinding required) of a similar nature that occur in participants that have received SPH3127 and the study team believe that participants would incur undue risk by continuing the study.
- Death (CTCAE grade 5) of any participant in which the cause of death is assessed to be related to study treatment and the participant was found to have received SPH3127.

Study termination requires that no additional participants will be administered study treatment. Participants who have already received study treatment will continue to be followed for safety through the remainder of the planned follow-up period.

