6.3 Premature Discontinuation

An enrolled subject is defined as having signed an informed consent, met all inclusion/exclusion criteria, been randomized to treatment and having received at least one dose of study drug.

A subject has the right to withdraw from the study at any time for any reason without prejudice or without jeopardizing their medical care. The Investigator must withdraw the subject from the study if the subject requests to be withdrawn.

The Investigator may discontinue a subject from the study when, in his/her judgment it is necessary for any reason, including any of the following:

- Adverse event (serious or non-serious);
- Failure to comply with the protocol;
- Requires a medication that is specifically prohibited by the protocol; or,
- It is in the subject's best interest.

The Investigator may also withdraw a subject upon the request of the Sponsor, or if the Sponsor terminates the study for clinical or administrative reasons.

If a subject is withdrawn from participation in the study, the reason(s) for discontinuation shall be documented. A subject who discontinues the study early (regardless of cause) will be requested to return to the clinic and have all the early termination assessments

performed. If a subject is discontinued from study due to an adverse event, the subject will be followed until the event is resolved or deemed clinically stable.

A subject that has been met all the eligibility criteria at Screening, but not at baseline (Day 1), will be replaced. A subject that has enrolled in the study (signed informed consent, met all inclusion/exclusion criteria, has been randomized and received at least one dose of study drug) that discontinues from the study (for any reason) will not be replaced.

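### The only grade-specific treatment stop in section 9.9 names Grade 3, not Grade ≥ 3, so the same lasting or recurrent drug-related event at Grade 4 has no named stop

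*Combined protocol and SAP*

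**What the plan says.** Section 9.9 grades adverse events by CTCAE v5.0 and places two bullets under one lead-in: "Study treatment should be permanently discontinued for the following".

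- The first names no grade. It applies when "The investigator believes that for safety reasons or tolerability reasons (e.g., AE), it is in the best interest of the participant" to stop.
- The second is the only participant-level bullet with a grade: "Any Grade 3 non-skin, drug-related AE lasting > 7 days, or recurs with the following exceptions for hypotension" without associated events, for diarrhea, and for symptoms of the colitis itself.

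The same section writes a threshold with ≥ in two other places. On unblinding: "Unblinding for individual patients may be warranted after consultation with the Medical Monitor for adverse events of CTCAE grade ≥ 3". On ending the whole study: "Two or more study drug-related ≥ Grade 4 AEs or SAEs (unblinding required) of a similar nature that occur in participants" given SPH3127, provided the study team also judges that going on would carry undue risk.

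Section 6.3 adds discretionary withdrawal, with no grade: "The Investigator may discontinue a subject from the study when, in his/her judgment it is necessary for any reason", and "The Investigator may also withdraw a subject upon the request of the Sponsor".

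**The concern.** A stopping rule tied to severity should be at least as firm for the worse event. Section 9.9 itself shows the order of the scale: death is grade 5, and study termination starts at Grade 4. Yet the one participant-level rule with a grade stops at exactly Grade 3.

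The issue is participant safety and consistent conduct. Safety and tolerability form the primary objective (section 2.1). About 20 sites are planned for 30 subjects (sections 5.1 and 5.2), an average of 30 / 20 = 1.5 subjects per site. Few sites will build up their own practice, so uniform stopping depends on the written rule. Treatment can also run for another 10 months in the extension, with scheduled visits every 8 weeks (section 6.2.7). Section 1.3.1 reports liver-test elevations more often than on placebo. They were generally mild and transient and do not show a Grade 4 risk, but they show why a clear rule for stopping is useful.

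**Working it through.** The plan states no figure on this point, so the check is a side-by-side reading. The test case is one participant with one drug-related event that is not a skin event, is not an excepted type, and lasts more than 7 days or recurs.

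| Rule | Grade named | Named stop at Grade 3? | Named stop at Grade 4? |
|---|---|---|---|
| 9.9, judgement bullet | None | No, depends on the investigator's view | No, depends on the investigator's view |
| 9.9, graded bullet | 3 | Yes | No, on a literal reading |
| 9.9, unblinding | ≥ 3 | No, concerns unblinding only | No, concerns unblinding only |
| 9.9, study termination for similar events | ≥ 4, or SAE | No, needs two or more events and a study-team judgement | No, same reason |
| 9.9, study termination for a death | 5 | No | No |
| 6.3, withdrawal | None | No, discretionary | No, discretionary |
| 9.4, pregnancy | None | Not applicable | Not applicable |
| 9.8, SAE reporting | None | No, notifies but does not stop | No, notifies but does not stop |

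**Other text that might fill the gap.** The opening sentence of 9.9 favours stopping when causality cannot be determined, but only for a participant who already meets the discontinuation criteria. It adds no Grade 4 trigger. Section 9.2 classes intensity as mild, moderate or severe, and section 10.3.2 lists laboratory results of Grade 2 or higher. Neither contains a stopping rule.

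**Result.** For the test case there is one named stop at Grade 3 and none at Grade 4.

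**Where the inversion ends.** For a first event of 7 days or less, a skin event or an excepted type, the graded bullet reaches neither grade. Both rest on judgement, so there is no inversion there.

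**Is the missing sign a conversion fault?** Probably not, because ≥ appears twice elsewhere in the same section.

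**Size.** No Grade 4 rate is given, so no expected number of affected participants can be calculated. With 10 subjects per arm (section 4.1), one extra discontinuation would be 1/10 = 10% of an arm and 1/30 = 3.3% of the trial.

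**The case against.** The strongest reply is that Grade 4 is already within the list. The judgement bullet stands under the same lead-in, covers any grade, and fits a lasting drug-related Grade 4 event better than almost anything else. The graded bullet is not automatic either, since someone must first judge the event drug-related. Other safeguards reach Grade 4: consultation with the Medical Monitor before any unblinding, SAE reporting within 24 hours where the event is serious, and the sponsor's power to request withdrawal. Grades also change over time. An event that spent more than 7 days at Grade 3 before worsening already meets the bullet. So, on a natural reading, does one that improves from Grade 4 to Grade 3 and stays there that long.

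Most of this stands, and it limits the weight of the point. A reader might infer that a participant with a Grade 4 event must stay on treatment, or that the protocol offers no way to stop. The documents do not support that, because the judgement bullet and section 6.3 both provide a route.

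The reply does not remove the inversion. It leaves the more severe event to judgement while the less severe one has a named stop. Calling the omission an obvious slip does not settle it either: if Grade ≥ 3 was meant, the text should say so, and if exactly Grade 3 was meant, the rule is harder to defend.

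**Conclusion.** The point holds as a wrong threshold in an operative safety rule, confined to drug-related events that are neither skin events nor excepted and that last or recur at Grade 4 without a qualifying course at Grade 3. It should be corrected.

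The practical effect is probably small. That rests on two assumptions: that Grade 4 events will be uncommon, which section 1.3.1 makes plausible by reporting no dose-limiting toxicity at any dose, and that most investigators would use the judgement bullet. Neither can be quantified from the documents.

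Two stronger conclusions are tempting. A reader might infer that the sponsor meant to exempt Grade 4. A dropped sign is the likelier explanation, but the documents do not show intent. A reader might also infer that the plan is in error for not stopping treatment at every drug-related Grade 4 event. That does not follow: for short, skin and excepted events the plan leaves Grade 3 and Grade 4 alike to judgement, which is a choice open to the sponsor.

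**What to change.** In the second bullet under the permanent-discontinuation lead-in of section 9.9, replace Grade 3 with Grade ≥ 3 and leave the rest of the bullet unchanged. This removes the inversion and matches the ≥ used elsewhere in the section.

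The cost is one changed term, made through a protocol amendment that needs IRB approval before it takes effect (section 14). It may cause an occasional extra treatment discontinuation. If that participant also leaves the study, the place is lost, since an enrolled subject who "discontinues from the study (for any reason) will not be replaced". Assessments, sample size and analysis do not change.

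As an option, the sponsor could add a bullet that stops treatment for any drug-related Grade 4 event of any type or duration, and confine the skin qualifier and the exceptions to Grade 3. That would be a new, stricter policy, to be decided on its own merits.

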9.10 Overdose

Any instance of overdose (suspected or confirmed and irrespective of whether or not it involved SPH3127) must be communicated to Shanghai Pharma Biotherapeutics USA Inc. or a specified designee. Details of any signs or symptoms and their management should be recorded including details of any antidote(s) administered.

10 STATISTICS

10.1 General Procedures

Descriptive statistical methods will be used to summarize the data from this exploratory study, with the term descriptive statistics referring to the number of subjects (n), mean, median, standard deviation (SD), minimum, and maximum for continuous data and frequencies and percentages for categorical data. Analyses will be performed at both the end of the main 8-week study and the active treatment extension. All statistical testing will be 2-sided and performed using a significance (α) level of 0.05. Statistical comparisons to placebo will be to the individual and pooled doses of SPH3127. The

statistical analyses will be conducted with the SAS software package version 9.1.3 or higher (SAS Institute, Inc, Cary, North Carolina).

10.2 Sample Size

No formal sample size and power calculations were made for this exploratory study.

10.3 Safety Analyses

The safety and tolerability of SPH3127 will be monitored by physical examinations, ECGs, clinical laboratory tests, vital signs, concomitant medications and AEs. Safety will be monitored through Day 63 (Main Study) or through the active treatment extension period, if applicable.

All treatment-emergent AEs will be summarized by treatment group and Medical Dictionary for Regulatory Activities (MedDRA) system organ class and preferred terms for each group of participants.

10.3.1 Adverse Events

The verbatim terms used in the CRF by investigators to identify AEs will be coded using the MedDRA. Treatment-emergent adverse events are AEs with onset during the treatment phase or that are a consequence of a preexisting condition that has worsened since baseline. All reported AEs will be included in the analysis. For each AE, the percentage of participants who experience at least 1 occurrence of the given event will be summarized by treatment group. Summaries, listings, datasets, or participant narratives may be provided, as appropriate, for those participants who die, or who experience a severe AE or a SAE.

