7.10 Adverse Events

Adverse events (AEs) will be recorded and monitored for all subjects who are enrolled in the study (sign an informed consent form and receive at least one dose of study drug).

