9.1 Documenting Adverse Events

The recording of AEs (regardless of their relationship to study drug) will begin with the Screening Visit until the Final Visit (Day 56) or Early Termination Visit. If the Investigator is made aware of an AE up to 7 days after the last dose of study drug the AE will be followed to resolution. For those patients who enter the optional active treatment extension, Investigator(s) will query patients for AEs when they visit the site to pick up their medication every 8 weeks. Investigator(s) will monitor each patient closely for AEs. At each visit, the Investigator will document all observed or volunteered AEs.

The Investigator(s) should always attempt to group signs and symptoms into a single term that constitutes a single unifying diagnosis. Adverse Events will be classified using the latest version of the Medical Dictionary for Regulatory Activities (MedDRA) classification system. AEs reported from the first dose of IP until 7 days after the last dose of IP will be considered as treatment-emergent AEs (TEAEs) and will be summarized descriptively. The Investigator's opinion of the association of each AE to study drug, the duration (date of onset / date of resolution), frequency, intensity, countermeasures (treatment), and the outcome of each AE will be documented. Each adverse event must be recorded separately. Multiple occurrences of a single PT in a patient will only be counted once at the maximum severity/grade. All AEs will be summarized by relatedness to IP. Any AEs leading to death or discontinuation of IP will also be summarized.

Any medical condition or laboratory abnormality that is present at subject screening and prior to the first dose of study drug should be considered as baseline, recorded in medical history, and should not be reported as an AE. However, if the medical condition worsens at any time during the study after the first dose of study drug it should be recorded as an adverse event.

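### The by-arm adverse event percentages in 10.3.1 are not limited to treatment-emergent events, so new-onset events between Screening and first dose can be counted against an arm

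*Combined protocol and SAP*

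**What the plan says.** Four places in the combined protocol and SAP bear on which adverse events reach the by-arm summaries.

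- **10.3 Safety Analyses** restricts the table: "All treatment-emergent AEs will be summarized by treatment group", by MedDRA system organ class and preferred term.
- **10.3.1 Adverse Events** defines the restricted set: "Treatment-emergent adverse events are AEs with onset during the treatment phase or that are a consequence of a preexisting condition that has worsened since baseline". It then drops the restriction: "All reported AEs will be included in the analysis". The percentage rule that follows is also unrestricted: "For each AE, the percentage of participants who experience at least 1 occurrence of the given event will be summarized by treatment group".
- **9.1 Documenting Adverse Events** sets the start of collection: "The recording of AEs (regardless of their relationship to study drug) will begin with the Screening Visit". It treats events reported from first dose to 7 days after last dose as treatment-emergent and summarises those descriptively. It also asks for all adverse events, without that limit, to be summarised by relatedness. A condition or laboratory abnormality present at screening and before first dose is baseline, belongs in medical history, and becomes an adverse event only if it worsens after first dose.
- **7.10 Adverse Events** ties recording to enrolment, which it defines as consent plus at least one dose: "Adverse events (AEs) will be recorded and monitored for all subjects who are enrolled in the study".

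The Schedule of Assessments (4.2) and the Screening visit list (6.2.1) both place adverse event collection at Day -28.

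**The concern.** Safety and tolerability is the primary objective (2.1), and adverse event incidence by arm is one of its main outputs. Two rules cover that output. A programmer who follows 10.3 leaves pre-dose events out. One who follows 10.3.1 as written puts them in.

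The interval in question is not quiet. The screening sigmoidoscopy, with bowel preparation, possible sedation and tissue sampling, takes place within 2 weeks after the Day -28 visit. An event that starts after that procedure was not present at the Screening visit, so on its plain wording the medical-history rule in 9.1 does not remove it. It would then be charged to a treatment the patient had not started.

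Pre-dose events cannot depend on the assigned treatment. On average they raise all three arms' percentages and shrink the contrast with placebo. In any one trial of this size they can also create or hide an imbalance by chance.

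**Working it through.** The plan gives no adverse event rate, effect size or power figure (10.2 states that no sample size calculation was made), so there is no stated figure to reproduce. The check is of the wording first, then of the possible size.

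**Which pre-dose events can enter**

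1. Present at Screening: sent to medical history by 9.1 and not reported as an adverse event unless worse after first dose. These stay out.
2. New onset between Screening and first dose: recording has begun under 9.1, and the medical-history rule does not clearly cover them. Under 10.3 they are out; under 10.3.1 read literally they are in.
3. Onset after first dose: in under either rule.

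Only the second group is at issue.

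**Length of the window.** Screening is Day -28 ± 2. The main-study treatment-emergent window under 9.1 is 56 + 7 = 63 days. The pre-dose share is 28/(28 + 63) = 28/91 = 31%, with a range of 26/89 = 29% to 30/93 = 32%.

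**One event.** With 10 patients per arm, a pre-dose event in a patient who does not have that term after dosing adds 1/10 = 10 points to that arm's percentage for the term.

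**Expected attenuation (assumed rates).** Let p be the placebo incidence over 63 days, assume a constant background hazard, a hazard ratio of 2 on drug, and every pre-dose event counted.

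- Treatment-emergent only: placebo p; drug 1 − (1 − p)^2.
- All reported: placebo 1 − (1 − p)^(91/63); drug 1 − (1 − p)^(2 + 28/63).

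| Assumed p | Treatment-emergent only | RR | RD (points) | All reported | RR | RD (points) |
|---|---|---|---|---|---|---|
| 10% | 10.0% v 19.0% | 1.90 | 9.0 | 14.1% v 22.7% | 1.61 | 8.6 |
| 20% | 20.0% v 36.0% | 1.80 | 16.0 | 27.6% v 42.0% | 1.53 | 14.5 |
| 30% | 30.0% v 51.0% | 1.70 | 21.0 | 40.3% v 58.2% | 1.45 | 17.9 |

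The risk difference shrinks by the factor 1 − q, where q = 1 − (1 − p)^(28/63) is the pre-dose risk: 4.6%, 9.4% and 14.7% in the three rows. The losses are 0.4, 1.5 and 3.1 points. If pre-dose events are kept out, q = 0 and nothing changes.

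**The case against.** The strongest reply is that the restriction to treatment-emergent events is already stated twice, in 9.1 and 10.3, and that 10.3.1 would have no reason to define the term if pre-dose events counted equally. On that reading, the inclusive sentence in 10.3.1 means only that events count regardless of relatedness, severity or seriousness. This is a fair reading, and an analyst who takes it will produce the right table. But 10.3.1 does not say so, and the relatedness summary in 9.1 is also unrestricted. The text permits both tables.

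The second reply concerns size, and much of it stands. The rates are assumptions. The percentages are tabulated event by event, and a 20% background for a single term is high. In absolute terms the loss is small: 1.5 points at 20% background is 0.15 of a patient in an arm of 10. The plan specifies no test of adverse events, so no stated error rate or power changes.

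A reader might infer more than the documents support:

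- That four weeks of all pre-dose findings enter the percentages. They do not: 9.1 sends conditions present at Screening to medical history.
- That drug washouts during screening add events. The exclusion criteria set look-back periods before randomization; no on-study washout is described.
- That 7.10 distorts the arm percentages by omitting patients who are never dosed. Such patients are outside the enrolled population, so they cannot affect those percentages. The conflict between 7.10 and 9.1 is a separate matter of collection.

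Sigmoidoscopy is also repeated within 2 days after Day 56, inside the treatment-emergent window of 9.1. Procedural events from that examination will remain in the percentages whichever rule is used.

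**Conclusion.** The inconsistency is real and limited. Taken literally, 10.3.1 admits new-onset events from the roughly 28 days before first dose into percentages that 10.3 and 9.1 reserve for treatment-emergent events. In expectation the effect is toward no difference from placebo; in a single arm of 10, one event is worth 10 points for its term.

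It would go too far to say that drug effects will be diluted by a known amount. Under the stated assumptions the risk ratio falls from 1.70–1.90 to 1.45–1.61 and the risk difference by about 0.4 to 3 points. Those figures rest on assumed backgrounds of 10% to 30%, a constant background hazard, a doubled hazard on drug and every pre-dose event being counted. The effect is zero if the analyst follows 10.3. The case for a change is that two rules govern a main output of the primary objective and that resolving them costs very little.

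The definitions of treatment-emergent also differ. Section 9.1 runs to 7 days after last dose and turns on when an event is reported. Section 10.3.1 turns on onset and refers only to the treatment phase. An event starting on Days 57 to 63 in a patient who does not enter the extension is therefore classified clearly by one and not by the other.

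**What to change.** 1. In 10.3.1, replace the inclusive sentence with a statement that every by-arm adverse event percentage, including the relatedness summary in 9.1, counts treatment-emergent events only.
2. List events with onset between consent and first dose separately, without treatment-group percentages.
3. Use one definition of treatment-emergent in 9.1 and 10.3.1. A definition by onset or worsening, with an explicit start and end, would settle both differences noted above.
4. Separately, reconcile 7.10, which limits recording to dosed patients, with 9.1 and the Schedule of Assessments, which start at Screening. State in 9.1 whether a condition that begins after the Screening visit but before first dose is an adverse event or medical history.

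The cost is one extra listing and minor wording changes. No visit, sample or test changes.
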